2.2.3.2 Clinical Trial Experience

A total of 160 adult patients have received MGA271 at doses up to 15 mg/kg, the maximum dose given in this study. One-hundred and forty-six of these patients received MGA271 in which MGA271 was given alone (no other chemotherapy was administered with MGA271). In other studies, 14 patients received MGA271 in combination with another drug for cancer treatment. To date, no person under the age of 18 has been treated with MGA271.

So far, the most important safety risk that has been identified with MGA271 is infusionrelated reaction (including reactions known as cytokine release syndrome [CRS]). Infusionrelated reactions are effects to a drug that may occur during or shortly after an infusion. Signs and symptoms of an infusion-related reaction may include fever, chills, nausea, vomiting, headache, muscle stiffness, rash, itching, low blood pressure, and difficulty breathing. Infusion-related reactions can be life threatening and, in rare cases, may cause death. Infusion related-reactions have occurred in a total of 37% (about 4 in 10) patients receiving treatment with MGA271. Most of the infusion-related reactions observed in patients receiving MGA271 have been mild to moderate in severity. However, six patients receiving MGA271 (< 4% of patients) have had serious or severe infusion-related reactions. These patients, some of whom were hospitalized for these reactions, recovered after receiving treatment with steroids, antihistamines, intravenous fluids, and other medications. One patient was discontinued from the study after experiencing a moderate infusion reaction.

The following were the most common side effects that were considered related to MGA271 administration and were seen in at least 1 of 10 participants. These side effects have been generally mild or moderate.

- Infusion-related reactions (including CRS) (37%)
- Fatigue (32%)
- Nausea (18%)
- Chills (14%)
- Vomiting (13%)

A total of 18 patients (11% or 1 in 10 patients) have experienced serious or severe side effects that were considered related to MGA271. Serious or severe side effects that occurred in 3 or more patients were infusion related reactions (6 patients, described above) and hyponatremia (which occurred in 3 patients).

There have not been any deaths considered related to the use of MGA271.

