- IV fluids, supplemental oxygen and bronchodilators should be considered as appropriate.
- If symptoms have resolved to baseline within 12 hours, a re-challenge may be considered at the next scheduled dose, with a 50% reduction of infusion rate. In addition, patients should be pre-medicated for this re-challenge and for any subsequent doses of MGA271 with the following: diphenhydramine hydrochloride 25-50 mg IV, oral acetaminophen 625 mg and hydrocortisone 25-100 mg IV. Patients who have a Grade 3 infusion reaction that does not resolve within 12 hours despite medical management should not receive further MGA271.
- Patients who experience a second Grade 3 infusion reaction at the time of rechallenge of MGA271 (irrespective of duration of first Grade 3 reaction), will permanently discontinue MGA271.
- Patients who experience a Grade 3 infusion reaction despite steroid premedication administration should permanently discontinue study drug.
- Report as an Immediately Reportable Event (IRE) within 24 hours.
- Report the event as a SAE, if appropriate.

6.4.4.4 Grade 4:

- Stop the infusion and disconnect the infusion tubing from the patient.
- TO AVOID EXACERBATION OF INFUSION REACTION OR CRS: DO NOT FLUSH THE TUBING.
- Administer diphenhydramine hydrochloride 50 mg IV, methylprednisolone 2-4 mg/kg IV (or more as considered appropriate), and other medications/treatment as medically indicated (e.g., an IL-6 receptor inhibitor or IL-6 inhibitor, an IL-2 receptor inhibitor, and/or an anti-TNF α antibody).
- Give epinephrine or bronchodilators as indicated.
- Support ventilation and blood pressure as indicated.
- Report as an IRE within 24 hours.
- Report the event as an SAE.
- Patients who have a Grade 4 infusion reaction will not receive further MGA271.

6.4.4.5 Grade 5:

- Report as an IRE within 24 hours.
- Report the event as an SAE.

All changes in the infusion of MGA271 including interruption of the infusion and its duration as well as reductions in infusion rate and duration must be recorded.

IRB#: IRB0010377

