10.2 Study Endpoints

10.2.1 Analysis of the primary endpoints

Safety and feasibility

Frequency of adverse events will be described using summary statistics. The proportion of patients with an adverse event will be reported with an exact binomial 95% confidence interval. All subjects receiving at least one dose of the study drug(s) will be evaluable for toxicity.

Early stopping rules for toxicity: Toxicity will be monitored closely and continuously. Any grade-3/4 local reactions (erythema, swelling, pain) attributable to MGA271 or Grade 3 infusion-related reaction or cytokine release syndrome that lasts ≥ 12 hours will be considered AEs for purposes of this stopping rule. A grade 4 infusion related reaction of any duration will be considered AEs for purposes of this stopping rule. If the risk of these adverse events appears to be higher than 33%, we will temporarily halt the study pending dose modification. Specifically, we apply a Bayesian toxicity monitoring rule that suspends the enrollment if the posterior probability of risk being larger than 0.33 is 65% or higher. The monitoring rule uses beta (1.5, 5.5) as prior distribution. This means that our prior guess at the proportion of toxicity is 21%, and there is 90% probability that this proportion is between 3% and 49%. The decision rule for toxicity stopping is as follows:

Study termination if:	3 AEs	4 AEs	5	6	7	8	9	10	11	12	13
In number of patients between:	3 - 4	5 - 7	8 - 10	11 - 12	13 - 15	16 - 18	19 - 21	22 - 24	25 - 27	28 - 30	31- 32

For example, we will interrupt the accrual if 3 patients have AEs among the first 4 receiving treatment. If 4 or more out of the first 5-7 patients have AEs, we will suspend accrual.

The operating characteristics of the stopping rule are shown below and are based on 5000 simulations:

Risk of AE	0.20	0.25	0.30	0.33	0.40	0.45
% of Time study stops	7.5%	18%	33.7%	46%	54.6%	73.3%
Expected sample size	30.3	28.2	25.3	22.8	21.2	17.3

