11.5 Study Termination or Modification

Adverse events and laboratory data from this trial will be assessed by the principal investigator and/or medical monitor on an ongoing basis. At least quarterly, data from the clinical database will be reviewed. The results of this review will be shared with all investigators and MacroGenics either in writing or as part of a teleconference. SAEs will be reviewed as they are reported to the principal investigator or project manager, and the medical monitor will make an assessment regarding the safety of continuing or modifying the study. This assessment will be shared with the investigators either in writing or as part of a teleconference. Should the assessment of either the principal investigator or the medical monitor be that the trial should be terminated, the study will then be closed to further accrual. Follow-up safety assessments will be performed for all patients who are taken out of the study prematurely.

IRB#: IRB0010377

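### The toxicity stopping-rule table understates stopping at its two highest risks: exact values are 72.4% at 0.40 and 86.6% at 0.45, not 54.6% and 73.3%

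*Combined protocol and SAP*

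**What the plan says.** The rule is under the early stopping rules for toxicity in section 10.2.1. Toxicity is monitored continuously, and the rule "suspends the enrollment if the posterior probability of risk being larger than 0.33 is 65% or higher". On the prior, the plan says: "The monitoring rule uses beta (1.5, 5.5) as prior distribution". A boundary table then gives the number of events that triggers action, from 3 events in 3 to 4 patients up to 13 events in 31 to 32 patients. Its row heading is "Study termination if". The worked example under it describes a pause: "If 4 or more out of the first 5-7 patients have AEs, we will suspend accrual".

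The operating characteristics follow, introduced by "The operating characteristics of the stopping rule are shown below and are based on 5000 simulations". (The same sentence introduces the feasibility table later in the section. The toxicity table is the one at issue.) The stated values are:

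| True risk | 0.20 | 0.25 | 0.30 | 0.33 | 0.40 | 0.45 |
|---|---|---|---|---|---|---|
| Stops, % | 7.5 | 18 | 33.7 | 46 | 54.6 | 73.3 |
| Expected size | 30.3 | 28.2 | 25.3 | 22.8 | 21.2 | 17.3 |

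**The concern.** The stopping row is uneven. It rises 12.3 points over the three-hundredths step from 0.30 to 0.33 (46 − 33.7), but only 8.6 points over the much wider step from 0.33 to 0.40 (54.6 − 46). A rule checked after every patient should not flatten just above its own threshold and then steepen again.

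Safety is a primary objective, and these two columns are the only ones clearly above the 33% limit. They are where a reader judges whether a 65% posterior cut-off is strict enough. As printed, they imply a 45.4% chance (100 − 54.6) of treating all 32 men without a halt when the true risk is 40%. A reader could wrongly conclude that the rule is weak, or carry the figures into a later protocol.

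**Working it through.** **Inputs.** Prior beta(1.5, 5.5), risk threshold 0.33, posterior cut-off 65%, continuous monitoring, boundary table and 5000 simulations, all from section 10.2.1. Maximum of 32 patients, from section 4.2 and the last band of the boundary table.

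**Step 1: boundaries.** After k events in n patients the posterior is beta(1.5 + k, 5.5 + n − k). The boundary b(n) is the smallest k for which P(risk > 0.33) is at least 0.65. For example, 3 events in 4 patients give 0.691 (halt), 3 in 5 give 0.607 (continue) and 4 in 5 give 0.812 (halt). No halt is possible before the third patient, because 2 events in 2 give 0.621. All 30 printed boundaries, n = 3 to 32, are reproduced.

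**Step 2: exact operating characteristics.** Let f(n, k) be the probability of having k events after n patients with no earlier crossing. For true risk p,

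f(n, k) = (1 − p) · f*(n − 1, k) + p · f*(n − 1, k − 1),

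where f* keeps only the states below the boundary. The stopping probability is the sum of f(n, k) over all n and all k ≥ b(n). The expected size is the sum of n times the probability of first crossing at n, plus 32 times the probability of no crossing.

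The simulation standard error of a stopping rate is √(P(1 − P)/5000). At 0.40 it is √(0.724 × 0.276/5000) = 0.63 points; at 0.45 it is √(0.866 × 0.134/5000) = 0.48 points.

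| True risk | Stops, stated | Stops, exact | Difference in simulation SEs | Size, stated | Size, exact |
|---|---|---|---|---|---|
| 0.20 | 7.5% | 7.7% | −0.4 | 30.3 | 30.2 |
| 0.25 | 18% | 17.7% | 0.5 | 28.2 | 28.2 |
| 0.30 | 33.7% | 33.7% | 0.0 | 25.3 | 25.2 |
| 0.33 | 46% | 45.4% | 0.9 | 22.8 | 23.0 |
| 0.40 | 54.6% | **72.4%** | −28.1 | 21.2 | **17.4** |
| 0.45 | 73.3% | **86.6%** | −27.5 | 17.3 | **13.8** |

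Four columns reproduce, so this is the algorithm the plan used. A separate simulation of 200,000 trials per risk gives 72.4% and 86.6% for the last two columns.

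**Step 3: size of the error.** Stopping is understated by 72.4 − 54.6 = 17.8 points at 0.40 and 86.6 − 73.3 = 13.3 points at 0.45. Expected size is overstated by 21.2 − 17.4 = 3.8 and 17.3 − 13.8 = 3.5 men. The chance of no halt is 27.6% rather than 45.4% at 0.40, and 13.4% rather than 26.7% at 0.45.

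**Step 4: could another reading give the printed figures?** The variants tried were caps of 16 to 31 patients, looks every 2, 3 or 4 patients, looks only at the start or end of each band, a later first look, no look at the last patient, and cut-offs from 0.60 to 0.80. None reproduces all six columns. Requiring more events than the printed count comes near the last two stopping rates (53.7% and 73.5%). It misses their expected sizes (23.6 and 19.9) and gives 1.7% at 0.20 against the stated 7.5%.

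**Step 5: likely cause.** Solving for the risk that yields each printed value gives 0.353 from both entries in the 0.40 column, and 0.403 and 0.402 from the two entries in the 0.45 column. The exact results at 0.35 are 53.4% and 21.4; at 0.40 they are 72.4% and 17.4. Against those risks the printed stopping rates are 1.7 and 1.4 standard errors away. Two rows pointing to the same shift suggest wrong column labels.

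**The case against.** The strongest reply is that the error has little practical consequence. The boundary table decides when accrual pauses, and it is correct. The performance table triggers nothing, and its columns up to the 0.33 threshold are right. The two wrong columns make the rule look weaker than it is, so anyone who accepted the printed figures would accept the true ones. Risks this high are also far from prior experience. Section 2.2.3.2 reports that six of 160 patients "have had serious or severe infusion-related reactions", which is 3.75%. Taking that as a rough proxy for the rule's event definition, the chance of ever crossing is about 0.03%. All of this stands, and it limits the weight of the point. It does not make the two columns correct.

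A reader might infer more from the heading "Study termination if": that a crossing ends the trial, or that it leads to a halt nobody is assigned to review. The documents do not support either reading. Section 10.2.1 describes halting, suspending or interrupting four times, twice in the worked examples directly under the table, so a pause is the intent.

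On review, section 11.5 says of SAEs that "the medical monitor will make an assessment regarding the safety of continuing or modifying the study", and section 6.4.4.3 says of grade 3 infusion reactions "Report the event as a SAE, if appropriate". Read alone, these could suggest that a counted event might escape review. But section 6.4.4.3 also makes every grade 3 infusion reaction immediately reportable within 24 hours. Section 11.5 opens with ongoing assessment of all adverse events by the principal investigator and/or the medical monitor, and either can have accrual closed. Section 9.3 adds Safety Monitoring Committee reporting and monthly meetings. An explicit link from the boundary to section 11.5 would be extra detail; its absence is not an oversight gap.

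**Conclusion.** The 0.40 and 0.45 columns are wrong as written, by 17.8 and 13.3 points for stopping and by 3.8 and 3.5 men for expected size. The result needs no outside figure. It assumes only what the section states: the printed boundaries, a look after every patient, a maximum of 32, and counting to the first crossing. The numerical error is certain under those inputs. The mislabelling explanation fits well, but the documents cannot confirm it.

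The error is conservative. It does not show that the stopping rule is weak or that patients face added risk. The boundaries, prior, threshold and sample size all stand. The feasibility table is not in question: the same method gives 1.3, 6.3, 29.4, 59.3 and 81.7% against the stated 1.1, 5.9, 29.2, 57.7 and 81.4%. The termination heading is a minor wording inconsistency. Overall the point should be fixed, as a calculation or labelling error.

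**What to change.** In the toxicity operating-characteristics table of section 10.2.1, replace the 0.40 column with 72.4% and 17.4, and the 0.45 column with 86.6% and 13.8. This keeps the printed risks and does not depend on the mislabelling inference. If the authors' simulation output confirms mislabelling, they could instead relabel the two columns 0.35 and 0.40 and add a true 0.45 column. Change the boundary table's heading to *Suspend accrual if:* so that it matches the text.

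The cost is four table entries and one heading, with no change to the conduct of the trial.

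### The last two columns of the toxicity stopping-rule table do not match their labelled risks: the rule stops 72.4% of trials at 40% risk and 86.6% at 45%, not 54.6% and 73.3%

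*Combined protocol and SAP*

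**What the plan says.** Section 10.2.1 (early stopping rules for toxicity) specifies the rule completely.

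- **Criterion:** the plan "suspends the enrollment if the posterior probability of risk being larger than 0.33 is 65% or higher".
- **Prior:** "The monitoring rule uses beta (1.5, 5.5) as prior distribution". It is summarised as "our prior guess at the proportion of toxicity is 21%, and there is 90% probability that this proportion is between 3% and 49" per cent.
- **Looks:** "Toxicity will be monitored closely and continuously".
- **Boundary:** the event counts are "Study termination if: 3 AEs 4 AEs 5 6 7 8 9 10 11 12 13", paired with patient ranges "3 - 4 5 - 7 8 - 10 11 - 12 13 - 15 16 - 18 19 - 21 22 - 24 25 - 27 28 - 30 31- 32". The worked example under the table shows that reaching or exceeding the count at any point in the range halts accrual.

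A table based on 5000 simulations follows, for true risks of 0.20, 0.25, 0.30, 0.33, 0.40 and 0.45. The percentage row is "of Time study stops 7.5% 18% 33.7% 46% 54.6% 73.3" and the row beneath it is "Expected sample size 30.3 28.2 25.3 22.8 21.2 17.3".

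**The concern.** The printed stopping percentages do not rise smoothly. From 0.30 to 0.33 they climb 12.3 points (33.7 to 46) over a step of 0.03. From 0.33 to 0.40 they climb only 8.6 points (46 to 54.6) over a step of 0.07. From 0.40 to 0.45 they climb 18.7 points (54.6 to 73.3) over a step of 0.05. A fixed boundary should not give a curve that flattens in the middle and then steepens again.

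The suspect columns are the two above the 33% limit, the only ones that show how the rule behaves when the drug is too toxic. Safety is a primary objective. A reader relying on the table would think the trial runs to completion 45.4% of the time at 40% risk and 26.7% of the time at 45% risk, and could judge the rule too weak on false figures.

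**Working it through.** **Inputs.** From section 10.2.1: prior Beta(1.5, 5.5), threshold 0.33, cut-off 0.65, a look after every patient, the printed boundary and 5000 simulations. The maximum of 32 patients is in section 4.2 and is where the boundary table ends.

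**Step 1: the prior.** The mean is 1.5 / (1.5 + 5.5) = 21.4%, and the central 90% interval is 3.0% to 49.5%. Both agree with the plan.

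**Step 2: the boundary.** After x events in n patients the posterior is Beta(1.5 + x, 5.5 + n − x). The boundary at n is the smallest x with Pr(risk > 0.33) ≥ 0.65. Examples:

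| n | Printed boundary | Posterior probability at the boundary | One event fewer |
|---|---|---|---|
| 3 | 3 | 0.772 | 0.525 |
| 4 | 3 | 0.691 | 0.436 |
| 5 | 4 | 0.812 | 0.607 |
| 32 | 13 | 0.698 | 0.570 |

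The printed boundary agrees with the criterion at every n from 3 to 32.

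**Step 3: exact operating characteristics.** Let f(n, k) be the probability of still accruing after n patients with k events, and p the true risk. Then

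f(n, k) = f(n−1, k)(1 − p) + f(n−1, k−1) p.

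All probability at or above the boundary at n is removed and counted as stopping at n. The stopping probability S is the sum of what is removed. The expected sample size is the sum of n × Pr(stop at n), plus 32 × (1 − S). The Monte Carlo standard error of a stated percentage is √(S(1 − S)/5000).

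| Risk | Stated stop | Exact stop | SE (points) | Difference / SE | Stated E[N] | Exact E[N] |
|---|---|---|---|---|---|---|
| 0.20 | 7.5% | 7.7% | 0.38 | −0.4 | 30.3 | 30.2 |
| 0.25 | 18% | 17.7% | 0.54 | 0.5 | 28.2 | 28.2 |
| 0.30 | 33.7% | 33.7% | 0.67 | 0.0 | 25.3 | 25.2 |
| 0.33 | 46% | 45.4% | 0.70 | 0.9 | 22.8 | 23.0 |
| 0.40 | 54.6% | **72.4%** | 0.63 | **−28.1** | 21.2 | **17.4** |
| 0.45 | 73.3% | **86.6%** | 0.48 | **−27.5** | 17.3 | **13.8** |

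The first four columns reproduce, which confirms the reading of the rule. The last two fail in both rows. A separate run of 200,000 simulated trials per risk gave 72.4% and 86.6%.

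**Step 4: a check without the recursion.** A trial with 12 or more events in its first 30 patients must have stopped by patient 30, because 12 is the boundary there. The overall stopping probability therefore cannot be below Pr(Binomial(30, p) ≥ 12). That is 56.9% at p = 0.40 and 76.7% at p = 0.45. Both exceed the printed 54.6% and 73.3%, so the printed values are impossible at the printed risks apart from simulation error. The shortfalls of 2.3 and 3.4 points are well beyond that error.

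**Step 5: which risks the printed figures fit.**

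| Printed column | Printed figures | Risk that fits | Exact figures there | Difference / SE |
|---|---|---|---|---|
| 0.40 | 54.6% / 21.2 | 0.35 | 53.4% / 21.4 | 1.7 |
| 0.45 | 73.3% / 17.3 | 0.40 | 72.4% / 17.4 | 1.4 |

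**Step 6: other readings.** Variants covered other maximum sample sizes (16 to 40), looks every 2 to 8 patients, looks only at the start or end of each range, no look before patient 5, cut-offs from 0.60 to 0.80, and a boundary one event higher. None reproduces all six columns. Raising the boundary by one event comes near the last two (53.7%, 73.5%) but gives 1.7%, 6.0%, 16.1% and 25.4% for the first four. Under the same method the feasibility table in the same section agrees within 2 points throughout.

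**The case against.** The strongest objection concerns weight. Accrual is governed by the posterior criterion and the boundary table, both of which are correct. No sample size, analysis or stopping decision uses the operating-characteristics table. Safety is also discussed at monthly meetings (section 9.3) and reviewed by the principal investigator and medical monitor (section 11.5). The error is conservative as well: the rule stops more often at high risk than the table says, so no patient loses protection. All of this stands. It makes the point a reporting error and not a safety defect.

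A second objection is that, if the columns are only mislabelled, the simulations were sound and just two header cells are wrong. That may be so. The fit to 0.35 and 0.40 is close but does not prove it, and the documents contain no simulation output to settle it. Either way, the table as printed attaches the wrong figures to 0.40 and 0.45.

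The arithmetic does not depend on a favourable choice of standard error. Using the largest standard error possible with 5000 runs, about 0.71 points, the gaps are still about 25 and 19 standard errors (17.8/0.71 and 13.3/0.71).

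**Conclusion.** The concern holds. At 40% risk the rule stops 72.4% of trials, 17.8 points more than stated, and expected enrolment is 17.4, or 3.8 patients fewer than stated. At 45% risk it stops 86.6%, 13.3 points more than stated, with expected enrolment of 13.8, or 3.5 fewer. The chance of failing to stop is 27.6% where the table implies 45.4%, and 13.4% where it implies 26.7%.

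This rests on the printed boundary, a look after each patient, a maximum of 32, independent patients with a constant risk, and a stop at patient 32 counted as a stop. Excluding that last look changes little: with a maximum of 31 the figures are 71.5% and 85.7%. Mislabelled columns are the likely explanation but remain an inference. The table should be corrected; the rule itself is sound.

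**What to change.** Have the trial statistician check the simulation code or output for the last two columns, then do one of the following.

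1. **Keep the risks 0.40 and 0.45** and print 72.4% / 17.4 and 86.6% / 13.8, or rerun figures that agree with these within simulation error. This changes four cells.
2. **Relabel the columns 0.35 and 0.40**, only if the output confirms that those were the simulated risks. This changes two header cells but leaves the table without a 0.45 scenario.

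The first option is cleaner because it keeps the scenario furthest above the limit. Neither changes the prior, the cut-off, the boundary, the sample size or the conduct of the trial.
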